3.10 Calculation of sample size

The calculation of the sample size on a group basing on previously participated in a similar occupational rehabilitation intervention for people with a BMI above 30 at Muritunet. The research question is leading for the sample size. The calculation is based on the time for data collection baseline and at the end of the intervention at Muritunet T3. The calculation is basing on apriority effect size, p value =0,05 and 80 percent statistical strength.

Goal of changing

1. Work; With a statistical power of 80,4 percent to achieve a clinical and a statistically significant change in 25 percent increasing work participation this study has to have 51 participants with two end point. The calculation is made out of 95 percent confidence interval (95% CL=18,05-31,95).
2. Weight reduction; With a statistical power of 80,2 percent to achieve a clinical and a statistically significant change in 11 kg weight reduction this study has to have 59 participants with two end point. The calculation is made out of 95 percent confidence interval (95% CL=6,82-15,18).
3. Quality of life; With a statistical power of 80,7 percent to achieve a clinical and a statistically significant change on 0,02 this study has to have 55 participants with two end point. The calculation is made out of 95 percent confidence interval (95% CL=0,025- 0,045). In the foam Quality of Life 15D, the SMR is the smallest clinical relevant change 0,015.

This calculation is done with the use of SPSS Sample Power program.

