The primary goal of this trial: What correlation is there between life style changing and work participation after participating in occupational rehabilitation on Muritunet?

Aims of the trial are:

1. Will changes in physical activity, diets, and life quality correlate with work participation?
2. Will changes in physical activity, diets, and return to work self-efficacy correlate with life quality?
3. Will changes in work participation, life quality, and diets correlate with weight changes?
4. What experience the participants as important factors to achieve lifestyle changes and work participation?

Work participation defined in this study is working full time or partial with an employer, permanent or temporary or as a student. The employee has to work coherently in 28 days without to receive social benefits.

Life quality defines in either in a subjective or an objective perspective [29]. In this study, the subjective perspective emphasizes the individual's positive, negative, cognitive and emotional experience that concern life quality.

Diet in this study is the intake of food and liquid that shall ensure a satisfying amount of calories, nutrient and prevent life style diseases.

Physical activity in this study is action made by musculature in a way that it results in increased energy consumption higher than resting.

3 Implementation

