3.9 Analyse

The goal of this study is to explore the correlation between life style changing and work participation. Four secondary issues will result in using different ways of analyzing the data material. In this way, each issue can be investigated on their own, but also analyzed with each other.

The primary analyzing approach for this study is multivariate logistics regression analysis with a focus on the correlation between several independent variables (X) and dependent variables (Y). In the main issue Y= work, and X= physical activity (x1), diets (x2) and life quality (x3). Work divides into three categories; a) full time working, b) part time working, c) not working. In the secondary issue, is Y= life quality and X= physical activity (x1), diets (x2), and the belief in managing (x3).

In the quality research, thematic methods will be used to analyze the interviews. This method can catch the significant complexity in the text and is the most usual way to analyze a text in qualitative research. This way of analyzing consist of six steps. 1. Transcribing data, 2. Reading and re-reading the data, 3. Coding, 4. Search after subjects, 5. Define and give a name to the subjects, and 6. Choose to illustrate examples of different issues.

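### The printed interval for work (18.05–31.95 with 51 people) is too narrow for the yes/no outcome in section 2, and it does not agree with the stated effect and power

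*Protocol*

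**What the plan says.** Protocol section 3.10 sets the general terms: "The calculation is basing on apriority effect size, p value =0,05 and 80 percent statistical strength". It ties the calculation to a before-after comparison: "The calculation is based on the time for data collection baseline and at the end of the intervention at Muritunet T3".

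Item 1 then gives the work target, "With a statistical power of 80,4 percent to achieve a clinical and a statistically significant change in 25 percent increasing work participation", with the requirement that "this study has to have 51 participants with two end point". The interval follows: "The calculation is made out of 95 percent confidence interval (95% CL=18,05-31,95". The item gives no unit, SD, baseline rate, gain or loss rate, reference value or test.

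Two other sections fix what kind of variable work is. In section 2: "Work participation defined in this study is working full time or partial with an employer, permanent or temporary or as a student". The same paragraph adds a rule of 28 continuous days of work without benefits, so a person either meets the definition or does not. In section 3.9, for the logistic regression: "Work divides into three categories; a) full time working, b) part time working, c) not working". Neither section defines work as a continuous percentage, such as percent of a full position.

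**The concern.** Item 1 is the planning calculation for work, the dependent variable of the main question in section 3.9. The interval is centred exactly on 25, so it presents itself as the precision around the planned effect. For a yes/no status the variance of a change follows from how many people move into and out of work, so the interval cannot be made arbitrarily narrow. The printed one looks narrower than 51 people can give.

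If so, a reader of section 3.10 is promised more precision on work than the defined outcome can deliver, and the stated power has no shown link to that outcome.

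**Working it through.** **Inputs.** From section 3.10: n = 51, change 25, interval 18.05 to 31.95, power 80.4%, alpha 0.05. Assumptions, because the protocol is silent: alpha is two-sided, 25 means absolute percentage points, the two measurements are paired in the same people, and the interval is for n = 51.

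**The printed interval.** Centre (18.05 + 31.95)/2 = 25.00; half-width (31.95 − 18.05)/2 = 6.95.

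**Step 1: narrowest interval for a yes/no outcome.** Let g be the proportion gaining work and l the proportion losing it, with g − l = 0.25. The variance of the paired change is (g + l − 0.25²)/n. It is smallest when nobody loses work (g = 0.25, l = 0):

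- SE = √((0.25 − 0.0625)/51) = √(0.1875/51) = 0.0606
- half-width = 1.96 × 6.06 = 11.9 points, so 13.1 to 36.9
- ratio to the printed half-width: 11.9/6.95 = 1.7
- n needed for 6.95 points: 0.1875 × (1.96/0.0695)² = about 149

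Other yes/no readings do no better. A single proportion of 25% in 51 people gives 13.1–36.9 (Wald), 15.2–38.3 (Wilson) or 13.9–39.1 (exact). Independent proportions with 51 at each time point give half-widths of 11.9 to 18.8. Even counting 102 observations, the minimum is 8.4.

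**Step 2: do interval, effect and power agree on a continuous scale?**

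- Implied SD = 6.95 × √51/c. With the t quantile (c = 2.009) it is 24.7; with c = 1.96 it is 25.3.
- For 25 against zero, the noncentrality is 25 × √51/24.7 = 7.2, and power exceeds 99.99%.
- Power of 80.4% at n = 51 needs a standardised difference of 0.402. That is 0.402 × 24.7 = 9.9, or 0.402 × 25.3 = 10.2: a difference of about 10, for example 25 against a reference near 15.
- Conversely, 80.4% power for a mean change of 25 from zero needs SD = 25/0.402 = about 62, which gives a half-width of about 17.5.

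The printed effect (against zero), interval and power therefore do not hold together on this scale either, unless an unstated reference value is supplied.

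**Step 3: power for the defined yes/no outcome.** McNemar test, n = 51, net rise 25 points, by full enumeration; half-width from the variance formula in step 1:

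| Leave work | Enter work | Exact test | Asymptotic test | 95% half-width |
|---|---|---|---|---|
| 0% | 25% | 99% | above 99.9% | 11.9 |
| 5% | 30% | 86% | 91% | 14.7 |
| 10% | 35% | 72% | 80% | 17.1 |
| 15% | 40% | 62% | 71% | 19.2 |

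A figure near 80% is within reach, but it depends on the test and on a loss rate that section 3.10 does not give. Where power is near 80%, the half-width is about 16 to 17 points, more than twice the printed 6.95.

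**The case against.** **The interval may not be for 51 people.** Section 3.10 says that the calculation rests on people who took part earlier in a similar programme, and the interval may be an input from that group, whose size is not given. The 1.7-fold ratio and the 149 would then not follow. This is possible, but it does not rescue the item. Its n, interval and power do fit together as a test of one mean against about 15, and the protocol states neither that scale nor that reference value.

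**The stated power can be reached on a yes/no outcome.** This stands. The asymptotic McNemar test gives 0.804 with 35% gaining and 10% losing work, and independent proportions of 0.15 and 0.40 give 81.7%. A reader might infer that 80.4% is impossible for the defined outcome, or that it needs a loss rate of about 7% or less. The first is wrong, and the second is true only of the exact test, which the protocol does not name.

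**The outcome in section 3.9 has three classes.** A reader might infer that the interval is impossible for any categorical outcome. That goes too far. Scored 0/50/100, a mean change of 25 has a minimum SD of 25 and a half-width of 6.86 (z) or 7.03 (t). The printed width is just attainable by z, if half the people move up exactly one step and nobody else moves. The protocol plans no such scoring.

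**The mismatch is not peculiar to work.** Item 2 concerns weight, a truly continuous variable. Its half-width of 4.18 with 59 people implies an SD of about 16 and power above 99.9% for 11 kg against zero, not 80.2%. This stands, and it shows that unstated reference values are part of the problem. Calling work continuous would not by itself explain the 80.4%.

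**The practical harm is limited.** The largest requirement in section 3.10 is 59, and at that size exact McNemar power is 91% and 79% for losses of 5% and 10%. The main question is also a correlation, not a before-after change. Both points lower the stakes, but neither makes the printed figure right.

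**Conclusion.** The point holds in a limited form. Read as the interval for the planned 51 participants, 18.05–31.95 cannot come from the yes/no outcome of section 2: the half-width is at least 11.9 points, against 6.95 printed. Separately, the interval, the 25-point effect and the 80.4% power do not agree with each other unless the tested difference is about 10. The power is unsupported for the defined outcome, not impossible.

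A reader might infer that the sponsor planned on a continuous variable such as percent of a full position. The implied SD of about 25 makes this plausible, but the protocol does not say so, and that variable alone would give power above 99.99% for 25 against zero.

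The conclusion rests on two-sided alpha, 25 read as absolute points, paired measurements and an interval for n = 51. The lower bound assumes that nobody leaves work; any losses widen the interval.

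**What to change.** Recalculate item 1 of section 3.10 for the yes/no outcome of section 2. State the test, the assumed proportions entering and leaving work, the resulting interval (no narrower than 13.1–36.9 with 51 people) and McNemar power over a range of loss rates, as in the table above.

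Alternatively, if percent of a full position was the planning variable, name it as the before-after work variable. Expected work time per week is already in the data packages of section 3.1. State its SD (about 25) and the reference value that was tested.

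Either route costs text and one recalculation, with no extra participants. The price is a less favourable stated precision on work if the yes/no outcome is kept.

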3.11 Organization and cooperation

Volda University College is responsible for this study. [name] is the project manager and the Ph.D. student. This study is a partnership between Volda UC and Muritunet. The participants are collected from an occupational rehabilitation program for people with a BMI above 30. Data from

baseline, T1, and T2 is from the participants stay at Muritunet. T3 happens where the participants live. T4 is from two different registers. The Ph.D. student is a full-time employee with Volda UC, but work 25 percent at Muritunet.

This study links to Regional Centre for Obesity Research and Innovation at St.Olavs Hospital in Trondheim, and the National Competence Centre for Work-Based Rehabilitation in Rauland.

3.12 User involvement

The user's voice in the project shall contribute to better planning and implementation of the intervention in the study. The user can participate in his or her experience, illuminate challenges, and share their own history. The project manager wishes to seek advice with the user about focus areas and questioners in the quality interview. It can also be useful to use the users to test the questions before the process with interviewing the participants. Muritunet does have other patients with similar challenges who can contribute in the process of quality assurance of the questions. Central Norway Regional Health Authority does also have professional users that can participate in this study.

3.13 Budget

The Central Norway Regional Health Authority is financing the occupational rehabilitation stays at Muritunet.

Volda UC. is funding the Ph.D. student.

3.14 Plan for the progress

	2016	2017	2018	2019	2020
Application Regional Committees for Medical and Health Research Ethics (REC)		X			
Application for finances	X				
Recruiting participants		X			
Data collection/ questioners	X		X	X	
Data collection/ journal		X			
Data collection/ register data					X
Status report			Årleg		
Articles			X	X	X

Results of the study are publishing in three articles.

3.15 Ethics

Regional Committees for Medical and Health Research Ethics (REC) has approved the study. It has its foundations in laws and guidelines for proper health research and the laws that apply to treatment in the Specialised Health Care services in Norway. Collected data shall be stored anonymous and locked after guidelines from the Personal Data Act, the Health Research Act and the Research Ethics Law. The participants give written consent before participating in the study.

Inconvenience

The participants may experience to fill the foams as bothersome. Individual follow-up of participants has reading and writing difficulties, challenges with the language or concentration problem.

Benefits

1. Participants in the study may increase self-efficacy, get more insight into own health and physical and mental disability through personnel in the Specialised Health Care services.
2. During the interview, participants can improve their understanding of their situation, perspective on their own possible to increase work activity and self-efficacy to returning or continuing to work.

4 Reference list

1. Sentralbyrå, S., *Helsefakta- Norge i verden. Fakta om helsetilstand og helsetjenester i Norge*. 2015, Statistisk Sentralbyrå: Oslo. p. 24.
2. Mannucci, E., et al., *Clinical and psychological correlates of health-related quality of life in obese patients*. Health Qual Life Outcomes, 2010. **8**: p. 90.
3. Neovius, K., et al., *Obesity status and sick leave: a systematic review*. Obes Rev, 2009. **10**(1): p. 17-27.
4. Organization, W.H., *World Health Statistics 2011*. 2011: p. 171.
5. Lehnert, T., et al., *Sick leave days and costs associated with overweight and obesity in Germany*. J Occup Environ Med, 2014. **56**(1): p. 20-7.
6. Janssens, H., et al., *The association between body mass index class, sickness absence, and presenteeism*. J Occup Environ Med, 2012. **54**(5): p. 604-9.
7. Lillis, J., *Acceptance and Commitment Therapy for the Treatment of Obesity-related Stigma and Weight Control*. PhD Psychology, 2007: p. 120.
8. Lazzeretti, L., et al., *Assessment of psychological predictors of weight loss: How and what for?* World J Psychiatry, 2015. **5**(1): p. 56-67.
9. Kleinman, N., et al., *Cohort analysis assessing medical and nonmedical cost associated with obesity in the workplace*. J Occup Environ Med, 2014. **56**(2): p. 161-70.
